8.7 Fibrinolysis labs

Blood samples will be collected at two time points during the study period to assess suppression of fibrinolysis with study dose of tranexamic acid. At time point one, blood will be collected prior to first dose of study drug to measure baseline fibrinolytic activity. At time point two, blood will be collected at one time point on Day 4-6 of treatment, at least six hours after last dose of study drug and prior to next dose of study drug, in order to assess the suppression of fibrinolysis when tranexamic acid is present at steady state. Samples should be processed and frozen within 4-8 hours of collection. Samples will be stored at the Children's Hospital of Pittsburgh. They will be batched together and shipped to UNC Chapel Hill where fibrinolysis assays will be completed in such a way as to allow for minimum shipments. A portion of each patient's frozen sample will remain at the Children's Hospital of Pittsburgh for use in later biomarker assays of fibrinolysis (unless only minimum quantity required by UNC Chapel Hill has been drawn, in which case all of the sample will be shipped.) At UNC Chapel Hill samples will be

stored until fibrinolysis assays have been completed and then will be disposed of. Samples at the Children’s Hospital of Pittsburgh will be stored indefinitely and used until exhausted. Study participants can request in writing that that samples no longer be used for research and any samples will be destroyed. Study sample may be used at later point for additional testing of the effects of tranexamic acid.

8.8 Laboratory procedures

The laboratory tests that will be performed as part of this study will be run in the hospital-based clinical laboratory and are standard in all hospital based clinical laboratories, with the exception of the fibrinolysis labs. Fibrinolysis lab samples will be processed at the Children’s Hospital of Pittsburgh and assays will be completed within research labs at the University of North Carolina Chapel Hill.

Table 4. Sample Requirements for Laboratory Assessments

Laboratory Test	Blood Volume	Urine Volume
CBC	1-3mL	
Serum Creatinine	1-2mL	
Bilirubin Level	1-2mL	
Urine Pregnancy		5-7mL
Serum Pregnancy	1-2mL	
PT/PTT/INR/Fibrinogen	2-4mL (same tube)	
Urinalysis		5-7mL
Fibrinolysis Labs	5-10mL	

8.9 Bleeding Assessment

Bleeding will be recorded using the WHO Bleeding score as the bleeding assessment tool. Bleeding assessments will be completed by means of a physical assessment of the patient, patient interview and a review of patient chart and laboratory data. Research staff will perform physical assessment and interview prior to reviewing the patient’s medical chart and laboratory data to allow an objective assessment. Nursing staff may provide additional details. Bleeding will be classified according to the scale as given below. More detailed assessment of bleeding score by organ system provided in the Appendix.

Table 5. WHO Bleeding Score

Grade 1	Grade 2	Grade 3	Grade 4
Minor Bleeding	Bleeding requiring intervention or treatment (eg nasal packing, bladder irrigation, platelet transfusions or medications to treat bleeding). Grade	Bleeding requiring red blood cell transfusion for treatment or requiring significant intervention to treat bleeding (eg endoscopy)	Bleeding that is fatal or life threatening

	2a: Grade 2 bleeding with the exclusion of skin manifestations		
--	---	--	--

8.10 Thrombotic Assessment

Assessment for thrombotic event will be performed via a review of medical chart notes and relevant imaging studies obtained within the time period from prior assessment.

9. Adverse Event Reporting

Whenever possible investigators should report adverse events as diseases or syndromes instead of reporting individual components of symptoms, signs, laboratory abnormalities or sequelae.

This study will be using the descriptive terminology developed by the National Cancer Institute for use in reporting adverse events: Common Toxicology Criteria for adverse events (CTCAE) version 4.03. These criteria can be found at: https://evs.nci.nih.gov/ftp1/CTCAE/CTCAE_4.03/CTCAE_4.03_2010-06-14_QuickReference_5x7.pdf. All Grade 3 or higher adverse events will be documented.

The CTCAE grading scale is applied to each adverse event term. Grades were developed using the following guidelines:

- Grade 1:** Mild; asymptomatic or mild symptoms; clinical or diagnostic observations only; intervention not indicated.
- Grade 2:** Minimal, local or non-invasive intervention indicated; limiting age-appropriate ADL.
- Grade 3:** Medically significant but not immediately life-threatening; hospitalization or prolongation of hospitalization indicated; disabling; limiting self-care ADL.
- Grade 4:** Life-threatening consequences; urgent intervention indicated.
- Grade 5:** Death related to AE.

The definitions that will be applied to adverse events recorded in this trial are given below:

Adverse event means any untoward medical occurrence associated with the use of a drug in humans, whether or not considered drug related.

Life-threatening adverse event or life-threatening suspected adverse reaction. An adverse event or suspected adverse reaction is considered “life-threatening” if, in the view of either the investigator or sponsor, its occurrence places the patient or subject at immediate risk of death. It does not include an adverse event or suspected adverse reaction that, had it occurred in a more severe form, might have caused death.

Serious adverse event or serious suspected adverse reaction. An adverse event or suspected adverse reaction is considered “serious” if, in the view of either the investigator or sponsor, it results in any of the following outcomes: Death, a life-threatening adverse event, inpatient hospitalization or prolongation of existing

hospitalization, a persistent or significant incapacity or substantial disruption of the ability to conduct normal life functions, or a congenital anomaly/birth defect. Important medical events that may not result in death, be life-threatening, or require hospitalization may be considered serious when, based upon appropriate medical judgment, they may jeopardize the patient or subject and may require medical or surgical intervention to prevent one of the outcomes listed in this definition.

Suspected adverse reaction means any adverse event for which there is a reasonable possibility that the drug caused the adverse event. For the purposes of IND safety reporting, “reasonable possibility” means there is evidence to suggest a causal relationship between the drug and the adverse event. Suspected adverse reaction implies a lesser degree of certainty about causality than adverse reaction, which means any adverse event caused by a drug.

Unexpected adverse event or unexpected suspected adverse reaction. An adverse event or suspected adverse reaction is considered “unexpected” if it is not listed in the investigator brochure or is not listed at the specificity or severity that has been observed; or, if an investigator brochure is not required or available, is not consistent with the risk information described in the general investigational plan or elsewhere in the current application, as amended.

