3.1 Primary Aims and Endpoints

Aim 1: To determine the safety and feasibility of the use of tranexamic acid in pediatric patients receiving chemotherapy or blood and/or marrow transplantation (BMT)

Endpoint: Incidence of adverse events, serious adverse events and death attributed to study drug; Number of patients screened eligible for enrollment and the rate of recruitment during study period

Aim 2: To evaluate the effectiveness of current dose of tranexamic acid for suppressing *in vitro* fibrinolysis

Endpoint: Measures of fibrinolytic activity at baseline (prior to tranexamic acid infusion) and at steady-state

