3.3 Safety Endpoints

Adverse events and serious adverse events will be monitored and collected from the time of activation of the study drug until a period up to and including 30 days after the last dose of the study drug. Adverse events and serious adverse events will to be assessed by CTCAE v.4.0 criteria and compared between study drug and placebo arms. The following events will specifically be compared across study arms;

- Incidence of thrombotic events (A thrombotic event is defined as venous or arterial thrombosis confirmed on imaging study, which may include Doppler US, CT scan, MRI or venography)
- Incidence of veno-occlusive disease (also known as sinusoidal obstruction syndrome)
- All cause-mortality, including incidence of death due to thrombosis

4. Population

Pediatric patients with hematologic malignancy or solid tumors receiving chemotherapy or undergoing BMT.

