8.4 Day 1 of Study Drug

- Hemostatic/Bleeding Assessment
 - If participant has had Grade 2 or higher bleeding within 48H of initiation of the study drug this should not be activated. They will be eligible for activation of the study drug later if bleeding later resolves.

- Thrombotic Assessment (via chart review)
- Laboratory Assessment (to be drawn prior to first dose of study drug)
 - CBC
 - Serum Creatinine
 - Urinalysis (if >72 hours from last Urinalysis)
 - Fibrinolysis study labs
- Data on Platelet Transfusions
 - Number of platelets transfused
 - Source of platelet transfusions (apheresis or whole blood)
 - HLA or cross-match compatible
 - Reason for transfusion
- Data on Red Blood Cell Transfusions
 - Number of units transfused
 - Reason for transfusion
- Adverse Event Assessment and Reporting – All Grade 3 or greater adverse events will be documented and followed
- Medication Review – Document new or discontinued medications

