Focal areas of retinal degeneration have developed in cats, dogs, and rats following oral or intravenous tranexamic acid at doses between 250 to 1600 mg/kg/day (6 to 40 times the recommended usual human dose) from 6 days to 1 year. The incidence of such lesions has varied from 25% to 100% of animals treated and was dose-related. At lower doses, some lesions have appeared to be reversible. Limited data in cats and rabbits showed retinal changes in some animals with doses as low as 126 mg/kg/day (only about 3 times the recommended human dose) administered for several days to two weeks. No retinal changes have been reported or noted in eye examinations in patients treated with tranexamic acid for weeks to months in clinical trials. Tranexamic acid should be discontinued if changes in examination results are found.

An increased incidence of leukemia in male mice receiving tranexamic acid at doses equivalent to as high as 5 g/kg/day may have been related to treatment. Hyperplasia of the biliary tract and cholangioma and adenocarcinoma of the intrahepatic biliary system have been reported in one strain of rats after dietary administration of doses exceeding the maximum tolerated dose for 22 months. Hyperplastic, but not neoplastic, lesions were reported at lower doses. Subsequent long-term dietary administration studies in a different strain of rat, each with an exposure level equal to the maximum level employed in the earlier experiment, have failed to show such hyperplastic / neoplastic changes in the liver. No mutagenic activity has been demonstrated in several in vitro and in vivo test systems.

Gastrointestinal disturbances (nausea, vomiting, diarrhea) may occur but disappear when the dosage is reduced. Allergic dermatitis, giddiness, and hypotension have been reported occasionally. Hypotension has been observed when intravenous injection is too rapid. A rare but important potential adverse effect is anaphylactic shock.

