11.1.1 Primary Endpoints

- Assessment of feasibility of recruitment by monitoring number of patients screened, number of patients eligible for enrollment and rate of recruitment (both start-up and ongoing) during study period
- Assessment of safety of tranexamic acid in this population by reported adverse events, serious adverse events and death.
- Assessment of the suppression of fibrinolysis by tranexamic acid will consider the difference in fibrinolytic activity in blood samples obtained from participants at the start of the study prior to receipt of the study drug and after achieving steady state.

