13.1 Data Management

Data will be collected in the manner described below. This study will use a paper based data collection system.

Case Report Forms (CRFs). Case report forms will be used to collect all subject study data during the course of the study. All protocol deviations will be documented and a justification for any missed assessments will be provided on the protocol deviation log. Completion of the CRFs will be on paper forms. All paper forms once completed will remain in a locked filing cabinet at the desk of the primary investigator. Any internal study team communications regarding the documentation of information on case report forms will be resolved via the secure UPMC email or phone communication and corrections will be made to appropriate CRFs. Any corrections to case report forms will be documented accordingly. The Investigator will allow the FDA, or other regulatory bodies to review the study files, subject CRFs, medical records and other study-related documents. Access to data will be limited to those who need access to perform their tasks.

Serious Adverse Events.

The Unexpected/Serious Adverse Event Form must be completed within 48 hours by the primary investigator, with appropriate attention paid to the grading, causality and expectedness of the event. In the absence of the responsible investigator the form should be completed and signed by a member of the site trial team. The responsible investigator should subsequently check the SAE form, make changes as appropriate and sign the

form.

Information about the following events will be collected and assessed:

- Serious adverse events, regardless of attributed relationship to study drug, that occur after study drug is activated
- Any unexpected adverse events (all grades), attributed as possible, probably or definitely related to the study drug.
- Causality of all serious adverse events

Follow-up: Following a Serious Adverse Event subjects must be followed-up until clinical recovery is complete and laboratory results have returned to normal or baseline, or until the event has stabilized. Follow-up should continue after completion of the study period if necessary. Follow up information may be provided on a separate form provided once a SAE report form has been received. The subject must be identified by trial number only, the subject's name will not be used on any correspondence.

14. Institutional Review Board (IRB)

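### Expected, non-serious Grade 1–2 effects of tranexamic acid need not be recorded in either arm, although the primary safety endpoint sets no grade limit

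*Combined protocol and SAP*

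**What the plan says.** The endpoint side carries no grade limit. Section 3.1 gives the safety endpoint as "Incidence of adverse events, serious adverse events and death attributed to study drug". Section 11.1.1 gives it as "Assessment of safety of tranexamic acid in this population by reported adverse events, serious adverse events and death". Section 3.3 says "Adverse events and serious adverse events will be monitored and collected from the time of activation of the study drug", continues this to 30 days after the last dose, and compares the arms using CTCAE.

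The collection side does carry one. Section 9 states "All Grade 3 or higher adverse events will be documented". Section 8.4 (Day 1) states "All Grade 3 or greater adverse events will be documented and followed", and the same instruction appears in Section 8.5 (Days 2–30) and Section 8.6 (the two contacts after study drug stops).

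Section 13.1 widens collection in two ways: "Serious adverse events, regardless of attributed relationship to study drug, that occur after study drug is activated", and "Any unexpected adverse events (all grades), attributed as possible, probably or definitely related to the study drug". Some outcomes have their own route. Section 3.3 compares imaging-confirmed thrombosis, veno-occlusive disease and mortality between arms with no grade threshold, and Section 8.9 records bleeding on the WHO scale from Grade 1 upwards.

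Section 9.4 lists the effects expected from the package insert. Among the milder ones are dizziness, nausea, vomiting and diarrhea, and it adds: "Allergic dermatitis, giddiness, and hypotension have been reported occasionally".

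**The concern.** The endpoint and the collection rules do not describe the same set of events. A reader of Sections 3.1 and 11.1.1 would expect an incidence of adverse events of any grade. A coordinator following Sections 8 and 9 would complete the form only from Grade 3, apart from the exceptions above.

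The exceptions also work in an odd direction. A mild event that is unexpected and possibly related is recorded. A Grade 2 event of a kind the protocol expects from the drug is not, unless it is serious. Low-grade events thus enter the data only through case-by-case judgments of expectedness and relatedness.

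This is a Phase I trial of 20 patients. Section 11.7 says it is not powered for bleeding and names establishing safety as a goal. Tolerability of repeated dosing is one of the main things it could hand to a larger trial, and the DSMB's interim review (Sections 11.6 and 12.2) relies on the same adverse-event data.

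**Working it through.** The plan gives no adverse-event rate and no figure on this point, so there is nothing of its own to reproduce. The check is to take one kind of event (listed in Section 9.4, non-serious, Grade 1 or 2) through each collection route.

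| Route | Section | Required to be recorded? |
|---|---|---|
| Routine adverse-event documentation | 8.4, 8.5, 8.6, 9 | No: threshold is Grade 3 |
| Serious events, any attribution | 13.1 | No: not serious by the outcome-based definition in Section 9 |
| Unexpected, at least possibly related, any grade | 13.1 | Normally no: Section 9 defines unexpected by absence from the known risk information, or a specificity or severity not listed there |
| Thrombosis, veno-occlusive disease, death | 3.3 | Only those outcomes |
| Bleeding, WHO scale | 8.9 | Only bleeding |

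No route requires it. This rests on Section 9.4, which is headed as the expected events, serving as the reference list for expectedness.

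Not everything in Section 9.4 falls through. Thromboembolism is assessed at any grade. Convulsions and anaphylactic shock would be recorded when Grade 3 or higher or serious. Visible hematuria and renal dysfunction are stopping criteria in Section 6.3. What remains is dizziness or giddiness, nausea, vomiting, diarrhea, allergic dermatitis and hypotension, when non-serious and Grade 1–2.

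To show the size, let p be the all-grade incidence of such an effect in one arm and s the share of cases that reach Grade 3. Both are assumptions. The arm size is n = 10 (Section 5.3), and patients are taken as independent.

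- Chance of at least one recorded case, all grades collected: 1 − (1 − p)^10.
- Same chance, Grade 3 or higher only: 1 − (1 − p·s)^10.

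For p = 0.30 and s = 0.20: 1 − 0.70^10 = 0.972, and 1 − 0.94^10 = 0.461.

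| p | Expected patients affected (10p) | All grades: at least one recorded | Grade 3+ only, s from 0 to 0.20 | Expected recorded, s from 0 to 0.20 |
|---|---|---|---|---|
| 10% | 1 | 65% | 0% to 18% | 0 to 0.2 |
| 20% | 2 | 89% | 0% to 34% | 0 to 0.4 |
| 30% | 3 | 97% | 0% to 46% | 0 to 0.6 |
| 50% | 5 | 99.9% | 0% to 65% | 0 to 1.0 |

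**The case against.** The best defence is that the rules form a deliberate tiered design. In children receiving chemotherapy or transplantation, mild nausea or dizziness is common and hard to attribute. A Grade 3 threshold, widened for serious and for unexpected related events, is a reasonable economy. The Grade 3 sentence can also be read as a minimum, and Section 11.3 bases adverse events on the medical record and patient report without a grade limit. Finally, Section 11.1.1 speaks of reported events, so some incidence can always be calculated from whatever is reported.

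Much of this stands. The threshold is a legitimate choice, and full Grade 1–2 capture is not needed. But a deliberate threshold belongs in the endpoint definition, and Sections 3.1, 3.3 and 11.1.1 do not state it. If lower grades may be recorded but need not be, the result is not an incidence.

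Several stronger readings are tempting, and the documents do not support them:

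- A reader might infer that nothing below Grade 3 is documented. Section 13.1 and the separate assessments of thrombosis, veno-occlusive disease and bleeding show otherwise.
- A reader might infer that the primary safety endpoint cannot be calculated at all. Deaths, serious events and Grade 3 or higher events are collected. What is missing is all-grade incidence for the listed milder effects.
- A reader might infer that the plan misses every effect it expects from the drug. The major ones are covered, as shown above.
- A reader might infer that the arms are forced to look alike, with zero cases in each. Uncollected events are missing, not zero, and any Grade 3 cases are still recorded.
- A reader might infer bias toward one arm. The rule is identical in both blinded arms.

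Nor would capture make the comparison decisive. With an assumed 4 of 10 against 1 of 10, the two-sided Fisher p-value is 2 × (252 + 2,100)/15,504 = 0.30. Comparisons at this size are descriptive.

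**Conclusion.** The mismatch is real and can be read directly from the text. The primary safety endpoint and Section 3.3 set no grade limit. Apart from serious events, unexpected related events and the separately assessed outcomes, documentation starts at Grade 3. Non-serious Grade 1–2 dizziness, gastrointestinal upset, allergic dermatitis and hypotension need not be recorded in either arm, so their all-grade incidence cannot be reported.

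The consequence is lost information, not a biased comparison. Under the assumed incidences of 10% to 50%, 1 to 5 patients per arm would be affected by a given effect and on average 0 to 1 would be recorded. Those figures depend on assumed rates, on 0% to 20% of cases reaching Grade 3, and on 10 patients per arm. The mismatch itself does not depend on them.

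**What to change.** Two changes are enough.

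1. In Sections 3.1, 3.3 and 11.1.1, restate the primary safety endpoint as Grade 3 or higher adverse events, serious adverse events, deaths, the unexpected related events of any grade in Section 13.1, and the separately assessed thrombosis, veno-occlusive disease and bleeding. Check that Sections 8.4 to 8.6, 9 and 13.1 then use the same terms. This costs only the wording.

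2. Add to the daily assessment form a short checklist, completed at any CTCAE grade, of the Section 9.4 effects not otherwise captured: dizziness, gastrointestinal upset, allergic dermatitis or reaction, and hypotension. Summarise it descriptively by arm, as counts out of the number treated. Thrombosis need not be on the list, since it is already assessed.

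Patients on study drug already have a daily interview and physical assessment for bleeding, so the cost is a few extra lines per day. Gastrointestinal symptoms will have a high background from chemotherapy, for which the placebo arm is the comparator. No dose or treatment rule changes.

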9.1 Frequency of Monitoring

The Investigator will review subject safety data as it is generated. The Investigator and Co-Investigator ([name]) will meet twice monthly to re-evaluate study goals, subject recruitment, data coding and retention, documentation and identification of adverse events, complaints and confidentiality of subjects. Additional Co-Investigators and research staff will be invited to attend. Meeting minutes will be made available for all research staff unable to attend. There will be an evaluation of the progress of the research study, including assessments of data quality, time lines, participant recruitment, accrual, and retention. The Investigator will also review the outcome and adverse event data to determine whether there is any change to the anticipated benefit-to-risk ratio of study participation and whether the study should continue as originally designed or should it be re-evaluated and changed.

9.2 Adverse Event Attribution.

Each adverse event is graded for its attributions to the study to determine whether an adverse event is related to a medical treatment by the following categories:

Table 6. Adverse Event Attribution

Attribution	Description
Not Related	Event clearly related to other factors
Possibly Related	Sequence of events is compatible with study drug, device or procedure but could have been produced by other factors
Probably Related	Sequence of event is compatible with the study drug, device or procedure and

	cannot be explained by other factors without much doubt
Definitely Related	Sequence of event is compatible with the study drug, device or procedure and beyond doubt cannot be explained by other factors

